8.6. Medications

It is recommended to discontinue the use of Class I and III antiarrhythmic medication by the end of the 90 day post-procedure blanking period.

Information regarding medications prescribed for anticoagulation, proton pump inhibitors, or to treat atrial arrhythmias (including adenosine and isoproterenol use during the ablation procedure), will be collected from subject enrollment through study exit, including the medication name, dose and frequency.

8.6.1. Class I and III antiarrhythmic medication use after the 90 day post-procedure blanking period

- Subjects may re-initiate, at any point during follow-up, a Class I or III antiarrhythmic medication that failed or was not tolerated prior to the ablation procedure at the same or lower dose.
- Initiation of a new Class I or III antiarrhythmic medication or a Class I or III antiarrhythmic medication dose increase after the 90 day blanking period will be considered a chronic treatment failure.
- All medications are permitted in the study except for investigational drugs that may confound the study results.

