12.5. Ancillary Objective #4

Characterize chronic treatment success of the ArcticLine Catheter in patients with demonstrated entrance block of all pulmonary veins.

Endpoint Definition

AF/AFL/AT episodes of at least 30 seconds duration from the end of the 90 day blanking period through the 6 month visit. Per section 8.6.1, the initiation of a new Class I or III antiarrhythmic medication or a Class I or III antiarrhythmic medication dose increase after the blanking period will be considered a chronic treatment failure. Also, a reablation for the treatment of recurrent AF/AT/AFL after the 90 day blanking period will be considered a chronic treatment failure.

Analysis Methods

Standard statistics will be used to summarize the percentage of patients without AF/AFL/AT and cumulative time spent in AF/AFL/AT as collected from the 6 month Holter data.

Note: Effectiveness data collected beyond the six month visit due to CIP Version 4 follow-up requirements will be adjudicated and included in the final report

Determination of Patients for Analysis

- All subjects undergoing an ArcticLine cryoablation procedure and who meet the following criteria will be included in the analysis:
 - Confirmed acute entrance block of all pulmonary veins
 - Confirmed acute posterior wall isolation (i.e. roof line and posterior wall line conduction block)
 - Confirmed acute bi-directional conduction block at the mitral isthmus, if applicable
 - Available 6 month Holter data
 - Note: An ArcticLine cryoablation procedure is considered to have occurred once the ArcticLine Catheter is introduced into the vasculature.
 - Note: For subjects who did not receive CTI ablation with ArcticLine Catheter, documented occurrence and treatment of typical right-sided cavotricuspid isthmus dependent atrial flutter during follow-up will not contribute to this endpoint.

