All subjects with index ArcticLine cryoablation procedures where the CTI line was attempted will be included in this metric.

7.26 Ancillary Objective 4

Characterize chronic treatment success of the ArcticLine Catheter in patients with demonstrated entrance block of all pulmonary veins.

Ancillary Endpoint #4

Chronic treatment success is the opposite of chronic treatment failure. Treatment failure is any of the following:

- AF/AFL/AT episodes of at least 30 seconds duration from the end of the 90 day blanking period through the 6 month visit.
- Per section 8.6.1 of the CIP, the initiation of a new Class I or III Antiarrhythmic Drug (AAD) after the 90 day blanking period, or a dose increase in a previously failed Class I or III AAD after the 90-day blanking period
- Reablation for the treatment of recurrent AF/AT/AFL after the 90 day blanking period

Note: For subjects who did not receive CTI ablation with ArcticLine Catheter, documented occurrence and treatment of typical right-sided cavotricuspid isthmus dependent atrial flutter during follow-up will not contribute to this endpoint. Subjects who (A) have “NOT APPLICABLE, CTI ABLATION NOT PERFORMED” indicated on all Procedure CRF’s, and (B) only have arrhythmia occurrences that the core lab determines to be typical CTI-dependent atrial flutter (as indicated in the recurrence type field on the core lab CRF; see below) will not be considered as chronic treatment failures on grounds of AFL recurrence. They may still experience chronic treatment failure for AF or AT, atypical atrial flutter, medication failures or repeat ablations outside of the blanking period.

Does the Assessment Indicate Recurrence of AF/ AFL/ AT	If Yes, Recurrence Type
LOV (2)	 ATRIAL FIBRILLATION  ATRIAL FLUTTER, CTI-DEPENDENT  ATRIAL FLUTTER, OTHER TYPE  ATRIAL TACHYCARDIA

Medication failures will be determined by calculating the pre-ablation maximum ongoing dose for each generic drug name (using TMS classification) for each patient. All medications described as “ongoing”

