will be assumed to continue for all future days a subject is under study, unless an update to the medication log indicates otherwise. Drug names not observed in a patient's failed medication history on the Baseline CRF, and not observed in the medication log will be assumed to have a pre-ablation maximum ongoing dose of 0 mg/day. Treatment failures will occur on the first day a subject's daily dose exceeds the calculated pre-ablation maximum ongoing dose. Therefore, any first use of a class I or III AAD after day 91 will constitute a failure. Any use of a new class I or III AAD within blanking will lead to a treatment failure at day 91 if the subject does not discontinue the drug prior to the end of the blanking period. Also, treatment failures will occur at day 91 for subjects with increases in AAD dose above the pre-ablation maximum ongoing dose that occur during the blanking period, if the dose is not reduced to or below the pre-ablation maximum before the blanking period ends. Treatment failures occurring after day 90 for increases in AAD dose above the pre-ablation maximum ongoing dose will be set to the date of the adjustment listed in the medication log.

Repeat ablations using radiofrequency (RF) ablation will be counted as chronic treatment failures on the date of the RF ablation, regardless of whether they occur within the 90 day blanking period. Repeat ablations using any energy modality occurring more than 90 days from the index procedure will be counted as chronic treatment failures. Repeat ablations observed through the repeat ablation CRF, as well as repeat ablations observed through the list of 'actions taken' in response to an AE, will both count toward ancillary endpoint #4.

Direct Current Cardioversion (DCCV) cardioversion is not a failure criterion; however, it is noted that when DCCV is observed (through actions taken fields on the Adverse Events CRF, for instance) it is most often performed in response to AF/AFL/AT, which is a failure criterion of ancillary endpoint #4. When a DCCV is observed, the study team should search for documentation of AF/AFL/AT, and the incident will be considered a chronic treatment failure only if the AF/AFL/AT motivating the DCCV is documented.

Analysis Methods

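### SAP 7.26 exempts typical flutter from the rhythm component in subjects without an ArcticLine CTI line but still counts drugs given for that flutter, contrary to protocol 12.5 and its own note

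*Protocol*

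**What the plan says.** Ancillary endpoint #4 (chronic treatment success) has a rhythm, a drug and a reablation component.

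- **General drug rule, protocol 8.6.1.** A chronic failure is "Initiation of a new Class I or III antiarrhythmic medication or a Class I or III antiarrhythmic medication dose increase after the 90 day" mark. The section also sets a limit on this: "Subjects may re-initiate, at any point during follow-up, a Class I or III antiarrhythmic medication that failed or was not tolerated prior to the" index procedure, provided that the dose is the same or lower.
- **Exemption, protocol 12.5.** The section restates the drug rule with a citation to 8.6.1. It then notes that, for subjects without ArcticLine CTI ablation, "documented occurrence and treatment of typical right-sided cavotricuspid isthmus dependent atrial flutter during follow-up will not contribute to this endpoint".
- **SAP 7.26, the note.** The SAP carries the same exemption, treatment included. It puts it into practice for subjects whose only arrhythmia is core-lab-confirmed typical flutter: they "will not be considered as chronic treatment failures on grounds of AFL recurrence". The next sentence says: "They may still experience chronic treatment failure for AF or AT, atypical atrial flutter, medication failures or repeat ablations outside of the blanking period".
- **SAP 7.26, the drug algorithm.** A failure occurs when the daily dose of a drug exceeds its pre-ablation maximum, which is zero for a drug not previously recorded, so "any first use of a class I or III AAD after day 91 will constitute a failure". A new drug or excess dose begun during blanking and not stopped or reduced by its end is a failure at day 91. Indication plays no part.
- **Data, protocol 8.6.** Medication information "will be collected from subject enrollment through study exit, including the medication name, dose and frequency".

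**The concern.** The exemption exists because typical flutter arises at a right atrial site that was not ablated with ArcticLine in these subjects. Protocol 12.5 therefore removes both the flutter and what is done about it from the endpoint. The SAP removes only the flutter.

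A subject whose sole recurrence is exempt flutter, and who is given a new Class I or III drug for it, is then a non-failure on the rhythm component and a failure on the drug component, for the same episode. The success estimate would depend on how an arrhythmia that is meant not to count happened to be managed. With at most 15 subjects, one classification is visible in the result.

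**Working it through.** **Passages side by side.** Take a subject without an ArcticLine CTI line whose only arrhythmia is typical CTI-dependent flutter.

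| What happens | Protocol 12.5 note | SAP 7.26 as written |
|---|---|---|
| Flutter recorded after day 90, no drug change | Not a failure | Not a failure |
| Previously failed drug restarted at the same or lower dose | Not a failure | Not a failure |
| New Class I/III drug started for the flutter after blanking | Not a failure | Failure |
| Dose raised above the pre-ablation maximum for the flutter after blanking | Not a failure | Failure on the adjustment date |
| New drug or excess dose begun for the flutter in blanking and continued past it | Not a failure | Failure at day 91 |

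The documents part company in the last three rows. The SAP also conflicts with itself there, because its note exempts treatment. Protocol 8.7 shows a similar intent: it excepts subjects without index ArcticLine CTI ablation from the rule that RF linear ablation is a treatment failure.

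**Can such a subject exist?** Yes. The synopsis requires CTI ablation only with a history of flutter or flutter induced at the procedure; otherwise it is optional. The number without a line is not given.

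**The plan's own figure.** There is none for this endpoint. The only precision figure, in SAP section 6, concerns the primary endpoint: a width of 32% for 1 event in 15. The Clopper-Pearson limits are 0.17% and 31.95%, a width of 31.8%, so it reproduces, but it does not bear on this point.

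**Effect on the estimate.** Inputs:

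- n is at most 15 (final cohort, SAP 7.7). It may be smaller, because SAP 7.26 requires confirmed acute block at the pulmonary veins and posterior wall, and at the mitral isthmus and CTI where applicable. The values 12, 10 and 8 are assumptions.
- f, the number of true failures, is assumed to be 3 for illustration.
- m is the number of exempt subjects counted as failures; m = 1 or 2 is an assumption.

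Without earlier censoring, the Kaplan-Meier estimate at 182 days is S = 1 − (f + m)/n, so each such subject lowers S by 1/n:

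- n=15: 1/15 = 6.7 points
- n=12: 1/12 = 8.3 points
- n=10: 1/10 = 10.0 points (for example 8/10 = 80% to 7/10 = 70%)
- n=8: 1/8 = 12.5 points

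For the SAP's interval (Greenwood standard error, log-log scale), write F = f + m. Then se = √[F / (n(n − F))] / |ln S|, and the limits are S^exp(±1.96·se). At n=15:

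| m | S | 95% CI |
|---|---|---|
| 0 | 12/15 = 80.0% | 50.0 to 93.1 |
| 1 | 11/15 = 73.3% | 43.6 to 89.1 |
| 2 | 10/15 = 66.7% | 37.5 to 84.6 |

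For m = 0: √[3/(15 × 12)] = 0.129 and |ln 0.8| = 0.223, so se = 0.579.

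**The case against.** The case on the other side has five parts.

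1. **The protocol alone is coherent.** Section 12.5 cites 8.6.1 and then adds the flutter note, which reads naturally as a specific exception to a general rule. A reader might infer that 8.6.1 itself misclassifies subjects; the documents do not support that. The defect lies in the SAP.

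2. **Not every drug counts.** A reader might infer that any drug treatment of the flutter produces a failure. It does not. Every subject has failed or not tolerated at least one Class I or III drug (protocol 7.3), and restarting such a drug within its earlier dose is not a failure. Under the SAP algorithm only a dose above the pre-ablation maximum counts. Cardioversion is not itself a failure criterion.

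3. **Indication may be recoverable.** A reader might infer that the exemption could never be applied to drugs because indication is not collected. Protocol 8.6 lists name, dose and frequency as included items, not as a complete list, and the full case report forms are not in these documents. Adverse event forms record treatment (protocol 10.3), the core lab form separates CTI-dependent flutter from other rhythms, and SAP 7.2.1 has study team personnel determine medication failures.

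4. **The scenario may not occur.** It needs no ArcticLine CTI line, typical flutter as the only recurrence, a new or escalated drug in use between the end of blanking and day 182, and entry to the acute-block analysis set. Subjects with known or inducible flutter should already have a line.

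5. **The exemption has a price.** A drug started for flutter may also suppress AF or AT, so exempting it could count as an ArcticLine success a subject who is on new antiarrhythmic therapy.

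The first three points narrow the finding to the SAP text and to new or escalated drugs. The fourth leaves the size conditional. The fifth is a genuine cost of the remedy. None removes the conflict: the SAP sets out the analysis to be run, and it does the opposite of what its own note says.

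**Conclusion.** The inconsistency stands, in limited form. SAP 7.26 contradicts protocol 12.5 and its own note by exempting typical flutter on the recurrence component only, while counting a new or escalated Class I or III drug given for that flutter, including one begun in blanking and continued to day 91.

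Each affected subject lowers the chronic success estimate by 6.7 points at n=15 or 10 points at n=10. This assumes that at least one such subject occurs and that there is no earlier censoring. It would be wrong to conclude that the reported estimate is in fact biased, since the documents do not show that anyone is affected. The endpoint is ancillary, with no hypothesis test and no decision rule attached, so the consequence is a misstated descriptive rate.

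**What to change.** Before the final analysis:

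- Reconcile the note and the drug algorithm in SAP 7.26 with protocol 12.5. A Class I or III start or increase documented as solely for typical CTI-dependent flutter, in a subject without an ArcticLine CTI line, would not count as a chronic failure. The wording should cover drugs begun in blanking and continued past it. Add a cross-reference to the 12.5 note in protocol 8.6.1.
- Establish the indication by source query, or from the actions-taken entries on the adverse event form, for the few relevant starts or increases. SAP 7.26 already asks the study team to look for the rhythm behind a cardioversion, so this is the same kind of check.
- List the subjects concerned and report a sensitivity estimate that counts them as failures.

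**Cost.** A short SAP revision, one cross-reference and a handful of queries in a 15-subject cohort whose procedures are complete. There are two downsides. Indication has to be judged from source, in an unblinded study, so the rule should be fixed before subjects are classified. The new drug may also suppress AF or AT and so raise apparent success, which the sensitivity estimate would make visible.

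This concerns endpoint classification only and proposes no treatment rule.

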8.7. Permissible Repeat Cryoablation

Repeat ablation, following the same procedure described in Section 8.4, is allowed one time within the 90 day post-procedure blanking period.

- Durability of all lesions, including pulmonary vein and linear lesions, will be assessed for gaps prior to re-ablating target locations.
- Ablation of linear lesions, outside of those described in Section 8.4, will be considered a treatment failure.
- Linear ablation using RF in the left or right atria will be considered a treatment failure with the exception of subjects who did not undergo CTI ablation with the ArcticLine Catheter in their index study procedure.
- Pulmonary vein ablation touch-up using RF will be considered a treatment failure.
- NIHSS Assessment
 - An NIHSS assessment will be administered to all subjects within 3 days prior to, including day of, repeat ablation procedure.
 - The NIHSS will be administered by study site personnel who have been certified to perform the NIHSS assessment and are delegated by their respective site to perform such assessment.
- Discharge procedures will be completed in accordance with Section 8.5

Repeat ablation procedures will be documented on an electronic case report form (eCRF). The subject's procedures and follow-up windows will continue based on the index ArcticLine Catheter ablation procedure date.

8.8. Scheduled Follow-up Visits

After receiving notice of a completed study procedure, Medtronic will provide the target dates and windows for each visit to the center. Should a subject miss a visit or the visit fall outside the pre-specified window, a study deviation must be reported and the original follow-up schedule maintained for subsequent visits.

Data analyses include follow-up visits, regardless of whether the visit occurs within the window. Therefore, a late visit is preferred over a missed visit but must be accompanied by a deviation. Follow-up visit windows are listed in Table 5 and are based on days after the index ArcticLine Catheter ablation procedure.

Table 5: Follow-up Schedule

Occurrence/ Visit	Window (Calculated days after the ablation procedure)	
	Window Start	Window End
Enrollment/Baseline ¹	-30 days	Day 0
Index ArcticLine Procedure	Day 0	Day 0
1 week phone or office	7 days	14 days
3 month	91 days	105 days
6 month	165 days	179 days
¹ Note: If the time between the consent date and the procedure exceeds 30 days, the subject must be re-evaluated against inclusion and exclusion criteria to ensure they still qualify for the study.		

Multiple modes of data collections may be employed to support the collection of required visit data at the 3 and 6 month visits such as: In office patient clinic visit, direct to patient contact (i.e. telephone, email, mail contact, etc.), and remote technology transmissions/uploads.

The following information is required to be collected at the follow-up visits:

8.8.1. One Week Phone or Office Visit

- Review medications
- Adverse event assessment
- Review symptoms suggestive of recurrent AF/AT/AFL

8.8.2. Three Month Visit

- Review medications
- Adverse event assessment
- Review symptoms suggestive of recurrent AF/AT/AFL
- 12 lead ECG
- Provide the subject with patient activated ambulatory monitoring equipment and provide instructions for monthly and symptomatic transmissions

8.8.3. Six Month Visit

- Review medications
- Adverse event assessment
- Review symptoms suggestive of recurrent AF/AT/AFL
- 12 lead ECG
- 24-hour continuous monitoring with Holter
- Collect or ensure return of ambulatory monitoring equipment

8.8.4. Unscheduled Office Visits

An unscheduled visit is defined as any unplanned cardiovascular-related office visit or early study exit at the study center that occurs between CIP required visits. If the subject exits the study early, an unscheduled office visit should occur. The following information is required to be collected at unscheduled follow-up visits:

- Review medications
- Adverse event assessment
- Review symptoms suggestive of recurrent AF/AT/AFL
- 12 lead ECG

8.8.5. Holter and Patient Activated Ambulatory ECG Monitoring

Market-released Holters will be distributed by a core lab to centers after activation has occurred. All subjects will wear a Holter in conjunction with their 6 month visit. Holters will be sent to the core lab after they have been worn by the subject. The core lab will be responsible for adjudication of atrial arrhythmias. The core lab will manage maintenance, calibration and tracking of the Holters.

Market-released Patient Activated Ambulatory ECG Monitors will be distributed by a core lab to centers after activation has occurred. All subjects will transmit monthly and symptomatic ECGs following their 3 month visit. The monitors will be returned to the core lab at the end of the study. The core lab will be responsible for adjudication of atrial arrhythmias. The core lab will manage maintenance, calibration and tracking of the monitors.

8.8.6. 12 Lead Electrocardiograms

All 12 lead ECGs will be sent to the core lab. The core lab will be responsible for adjudication of atrial arrhythmias. Copies of additional source documents may be requested.

8.9. Assessment of Safety

The primary safety objective is based on the Adverse Event data collected. Further information on the collection of Adverse Events is discussed in Section 10.

8.10. Recording Data

The study will collect data using an electronic data management system for clinical studies. Centers will enter data onto case report forms (CRFs) within the electronic database. The Holter/Patient Ambulatory Monitoring/12-lead ECG core lab will also provide data in the electronic database.

Data reported on the CRFs shall be derived from source documents, which may include worksheets, patient medical records and ECG data. These source documents must be maintained by the center personnel. Further detail on data management is provided in Section 14.2.

8.11. Deviation Handling

A study deviation is defined as an event within a study that did not occur according to the CIP or the Clinical Trial Agreement. Prior approval by Medtronic is expected in situations where the Investigator anticipates, contemplates, or makes a conscious decision to deviate. If the deviation affects subject's rights, safety and well-being, or the scientific integrity of the study, prior approval from IRB/REB/MEC may also be required, depending on local requirement. Prior approval is not required when a deviation is necessary to protect the safety, rights or well-being of a subject in an emergency or in unforeseen situations beyond the Investigator's control (e.g. subject failure to attend scheduled follow-up visits, inadvertent loss of data due to computer malfunction, inability to perform required procedures due to subject illness). Subjects' failure to submit ambulatory monitoring transmissions per the CIP does not require a deviation to be reported. Ambulatory monitoring transmission compliance will be tracked by Medtronic personnel and the Core Lab.

For medically justifiable conditions which preempt a subject's ability to complete a study-required procedure, it may be permitted to report only one deviation which will apply to all visits going forward. This may also apply for other unforeseen situations (e.g. the subject permanently refuses to complete a study required procedure and the data will not contribute to the primary endpoint analysis). However, prior approval from Medtronic is required for such situations.

All study deviations must be reported on the eCRF regardless of whether medically justifiable, pre-approved by Medtronic, an inadvertent occurrence, or taken to protect the subject in an emergency. The deviation description must be recorded with an explanation for the deviation.

In the event the deviation involves a failure to obtain a subject's consent, or is made to protect the life or physical well-being of a subject in an emergency, the deviation must be reported to the IRB/REB/MEC as well as Medtronic within five (5) working days. Reporting of all other study deviations should comply with IRB/REB/MEC policies and/or local laws and must be reported to Medtronic as soon as possible upon the center becoming aware of the deviation. Reporting of deviations must comply with IRB/MEC policies, local laws, and/or regulatory agency requirements.

Medtronic is responsible for analyzing deviations, assessing their significance, and identifying any additional corrective and/or preventive actions (e.g. CIP amendment, conduct additional training, terminate the investigation). Repetitive or serious Investigator compliance issues may result in initiation of a corrective action plan with the Investigator and center, and in some cases, necessitate suspending enrollment until the problem is resolved or ultimately terminating the Investigator's participation in the study. Medtronic will provide center-specific reports to Investigators summarizing information on deviations that occurred at the investigational center on a periodic basis.

